**11.2. Procedures for orderly termination:**

If a participant must be withdrawn from all study procedures the study staff would contact the family to explain the cause for study withdrawal and finalized study termination.

**11.3. Procedures that will be followed when subjects withdraw from the research, including partial withdrawal from procedures with continued data collection and withdrawal from data/specimen banking:**

Full Withdrawal: If a participant must be withdrawn from all study procedures the study staff would contact the family to explain the cause for study withdrawal and finalized study termination.

Partial Withdrawal: If a participant partially withdraws from the procedures, study staff would contact the family to discuss family's interest in participation. If the family is interested, the study procedures will be continued, if the family is not interested, this will be considered a full withdrawal.

**12. Risks to Subjects****12.1. Reasonably foreseeable risks to subjects (include each study population, each arm, and optional procedures):**

This study is minimal risk. There are potential risks around emotional distress, time commitment, and confidentiality. Although asking about physical symptoms and mood/behavior does not typically result in any distress, there is a small risk of emotional

distress. There is a potential risk of loss of confidentiality. Some of the questionnaires include questions that could uncover depression or suicidal ideation. See below for plan.

**12.2. Procedures with unforeseeable risks:**

There are no anticipated harms associated with participating in this study. Participants may get upset when talking about their pain from SCD. This risk will be discussed when consent is provided, and participants will be reminded that if they become upset at any time during the course of the study they can talk to the research assistant and their health care team (for example, nurse, social worker, or psychologist).

Participants may be inconvenienced with the amount of time required to participate in the study (2 months + 6 month follow up).

**12.3. Procedures with risks to an embryo or fetus should the subject be or become pregnant:**

N/A

**12.4. Risks to others who are not subjects:**

N/A

**12.5. Procedures performed to lessen the probability or magnitude of risks:**

Participants will be advised they can skip any questions they feel uncomfortable answering. To support confidentiality, adolescents will be asked to complete questionnaires independently. We will make every effort to protect this data. For example, all data will be coded with a unique ID number. Participants will be informed of their right to refuse to participate in any part of the data collection and given the phone numbers of the PI and the Seattle Children's IRB in the event that they desire further information or would like to issue a formal complaint. In the course of the study, we may become aware that participants are an imminent threat to themselves. The PI will be available 24 hours a day to be called via cell phone to address crisis questions and the study team will follow the Critical Incident Protocol. Crises that are high risk and imminent will be acted upon immediately with staff linking participants to appropriate crisis services. Parent contact information will be used when appropriate. Lower risk and less imminent cases are also reviewed by the clinically responsible PI. All actions taken will be documented on a case report form and reported to the IRB.

**13. Potential Benefits to Subjects**

**13.1. Potential benefits that individual subjects may experience from taking part in the research:**

No immediate and direct benefits to individual participants are expected. However, some participants may improve their pain self-management skills from participating in education control or active intervention. The information acquired from this study also will allow researchers and health care providers to have a better understanding of the psychosocial factors associated with pain and functioning in SCD and how to best teach self-management skills. The information from this proposed project may be useful to clinicians who deal with SCD patients and families, who often request information about how to better manage pain and in the design of future interventions.

**14. Data Analysis/Management**

**14.1. Data analysis plan, including statistical procedures:**

Data analyses will be performed using SPSS v20.0 and SAS v9.3. Distributions of primary and secondary outcome variables at each time point (and on difference scores between time points) will be examined first with summary statistics and graphical tools. For outcome variables with highly skewed distributions, we will either apply transformation or non-parametric test procedures. Preliminary work will also involve computation of scale reliabilities (e.g., internal consistency using Cronbach's alpha) of all of the self-report measures. The pilot RCT analysis will be an intent-to-treat analysis including all randomized subjects.

### **Analytic plan for Aim 1**

Feasibility will be determined by calculating rates of accrual, drop out, compliance, and missing data with 95% CI's. Criteria for feasibility success will be based on previous studies by our group: accrual rates >70%, attrition rates <20%, minimal technical difficulties (i.e., reported by <10%), high acceptability and satisfaction (item mean score of 4 on AES), adherence rates >80%, and minimal missed responses. In Aim 1, we will also determine preliminary efficacy of the intervention. To account for clustering due to repeated assessments within individuals, generalized estimating equations (GEE) will be used. Interaction terms will be used to compare the mean change from pre-treatment to post-treatment for the *iCanCope* group with the corresponding mean change for the *Attention Control Education* group. Single degree of freedom contrasts will test if there is a statistically significant change in pain and coping from pre-treatment to immediate post-treatment for the two groups separately; additional contrasts will be computed to test if there is a statistically significant mean change from baseline to the 6-month follow-up for each group. Secondary treatment outcomes (physical and emotional function, HRQL) will also be examined using GEE to test significant mean changes over time and between groups by using interaction terms and contrasts. Treatment fidelity will be assessed by examining differential attrition (completers vs. non-completers) between and within groups using chi-squared tests and logistic regression models.

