**10.4. Power analysis:**

Based on prior and current study experience, and the pool of available study candidates, we plan to enroll a total of 160 subjects into the pilot RCT. With attrition conservatively estimated at 20% we expect a final sample size of 128. This proposed sample size is based on the following power calculation using preliminary data from investigator experience with prior pain trials and published trials in SCD:

Calculations are based on expected differences in youth pain-related disability and pain intensity. Group sample sizes of 52 and 52 achieve 84% power to detect a difference of 1.0 in pain-related disability between the two treatment conditions, with three assessments, AR(1) covariance structure, SD=4, ICC=0.2, and alpha=0.05. If the difference is 1.5 between treatment arms, then 52 per group achieves 99% power with the same assumptions. For pain intensity, group sample sizes of 49 and 49 achieve 80% power to detect a difference of 0.75 in pain intensity (average over three time points) in a design with 3 repeated measurements having a AR(1) covariance structure, SD=2, ICC=0.2 and 0.05 alpha.

**11. Withdrawal of Subjects****11.1. Anticipated circumstances under which subjects will be withdrawn from the research without their consent:**

The PI may decide to withdraw participants from the study if a family is not able to comply with study procedures or do not understand study instructions.

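### The efficacy GEE has no stated working correlation or missing-data method, although 20% attrition is expected; dropout that relates to severity differently in the two arms could bias the group-by-time contrast

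*Combined protocol and SAP*

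**What the plan says.** The Analytic plan for Aim 1 (section 14.1) names a single method for the primary and secondary outcomes: "To account for clustering due to repeated assessments within individuals, generalized estimating equations (GEE) will be used". Two kinds of test follow from it. The first is between arms: "Interaction terms will be used to compare the mean change from pre-treatment to post-treatment" in the intervention group with that in the control group. The second is within each arm: "Single degree of freedom contrasts will test if there is a statistically significant change in pain and coping" from pre-treatment to post-treatment for the two groups separately, with further contrasts to the 6-month follow-up.

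On the analysis set, section 14.1 says: "The pilot RCT analysis will be an intent-to-treat analysis including all randomized subjects". On losses, section 10.4 says: "With attrition conservatively estimated at 20% we expect a final sample size of 128". Attrition below 20% is also one of the feasibility criteria.

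The only planned look at who drops out is this: "Treatment fidelity will be assessed by examining differential attrition (completers vs. non-completers) between and within groups using chi-squared tests and logistic regression models". It carries a fidelity label, and nothing says what happens to the efficacy estimate if it finds a difference.

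The documents give no working correlation for the GEE, no weights, no imputation, no stated missing-data assumption and no sensitivity analysis.

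**The concern.** GEE solves its estimating equations on the visits that were observed. In general this gives consistent estimates only if the chance of being observed does not depend on outcomes, beyond what the covariates in the model explain. With one participant in five expected to be lost, that condition matters, and the plan neither states it nor offers protection if it fails.

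Dropout that differs by arm is conceivable here. Section 5.2 gives the experimental arm six to eight web modules plus an app with symptom and goal tracking, and gives the control arm a static library site. Section 11.1 lets the PI withdraw families who cannot comply with study procedures, and those procedures differ by arm. If more disabled youth leave one arm more readily, the youth left in that arm look better at follow-up for reasons unrelated to treatment. The between-arm contrast then shifts and its type I error rises. If the same selection acts in both arms, the between-arm contrast is largely protected, but each arm's own change from baseline is still distorted, and the plan tests those changes separately.

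**Working it through.** **Plan's own figure.** 160 × (1 − 0.20) = 128, as section 10.4 states.

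**Inputs.** From section 10.4: disability SD 4, correlation (ICC) 0.2, target difference 1.0, 20% attrition, 160 enrolled. Equal arms are implied there, so 80 per arm and 80 × 0.8 = 64 retained. Assumed here: dropout odds double per SD of baseline disability; all 20% is lost before T2 (the plan does not divide attrition by visit); correlations of 0.5 and 0.7 as alternatives; no true effect; independence working correlation.

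**Bias.** With independence and a saturated group-by-time model, the estimated change in an arm is the observed T2 mean minus the T1 mean of everyone. Let z be standardised baseline disability and p(z) the dropout probability, logistic with slope ln 2 = 0.693 and intercept −1.52 (which gives 20% overall). Then

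E[z | retained] = −0.693 × E[p(1 − p)] / 0.8 = −0.693 × 0.149 / 0.8 = −0.129.

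The bias in that arm's change is SD × ρ × (−0.129) = −0.515ρ. The between-arm bias has this size if only one arm is affected, twice this size if the patterns are opposite, and is zero if both arms behave alike.

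**Type I error.** Variance of the contrast ≈ 2 × 16 × (1/64 + 1/80 − 2ρ/80), so the standard error is 0.860, 0.707 and 0.583 at ρ = 0.2, 0.5 and 0.7. The rejection rate is P(|Z + bias/SE| > 1.96).

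| ρ | One arm only: bias, type I | Opposite patterns: bias, type I | Alike in both arms |
|---|---|---|---|
| 0.2 (plan) | 0.10, 5.2% | 0.21, 5.7% | 0 |
| 0.5 | 0.26, 6.5% | 0.52, 11.3% | 0 |
| 0.7 | 0.36, 9.5% | 0.72, 23.6% | 0 |

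Simulation of 6,000 trials per scenario agrees. One arm: bias 0.11, 0.25, 0.36. Opposite: 0.21, 0.52, 0.73, with type I error 5.9%, 11.4%, 22.7%. A likelihood estimate on the same data had bias of about 0.01 or less and type I error of 4.3-5.3%.

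**Same data, exchangeable working correlation** (3,000 runs, still unweighted). Opposite-pattern bias was 0.01, −0.03, −0.04, with type I error 5.5-5.7%. One-arm bias was at most 0.03, with type I error 5.4-5.7%.

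**Three visits, pain intensity.** SD 2 and true effect −0.75 are from section 10.4. A steeper dropout slope (log-odds 1 per SD of pain), 10% lost before T2 and 20% by T3 are assumed. T3 bias under independence, at ρ = 0.2 / 0.5 / 0.7:

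- Dropout alike in both arms: contrast about 0; within-arm change biased by −0.04 / −0.14 / −0.22.
- Pain-related dropout in control only: 0.05 / 0.14 / 0.23, or 6% / 19% / 30% of 0.75.
- Opposite patterns: 0.10 / 0.29 / 0.45, or 13% / 38% / 60%.

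In these three scenarios an exchangeable working correlation leaves 0.04 or less, the correct AR(1) leaves about 0, and inverse-probability weights with the true dropout probabilities leave 0.003 or less.

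**Dropout on unobserved current pain, control only.** Independence gives 0.24 to 0.32 at T3. A correct AR(1) model still leaves 0.17 to 0.23.

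**The case against.** The strongest reply is that the size of the problem depends on a working correlation the plan does not choose. GEE is introduced precisely to handle correlation within individuals, and section 10.4 assumes AR(1) covariance for power, so independence is the least favourable reading. With an exchangeable or AR(1) structure, ordinary GEE does nearly as well as the likelihood model when dropout depends on observed outcomes. That stands. It limits the size of the problem but does not close the gap: the AR(1) assumption belongs to the power calculation and is not carried into the analysis plan, and no working correlation rescues the case of unobserved pain.

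It is also fair that at the plan's correlation of 0.2 the effect is small, that nothing in the documents points to opposite patterns in the two arms, and that this is a pilot whose efficacy aim is called preliminary. Even so, the plan commits to between-arm comparisons and significance tests.

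Three stronger readings go beyond the documents:

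- A reader might infer that the plan chose unweighted GEE. It is silent; it neither specifies nor excludes weights.
- A reader might infer that youth without follow-up fall outside the intent-to-treat analysis. Section 5.2 collects T1 before randomisation, so youth with only T1 data enter available-data GEE just as they enter a mixed model.
- A reader might infer from the attrition comparison that the sponsor already expects informative dropout. The plan presents it as a fidelity check, and section 10.4 calls 20% conservative.

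**Conclusion.** The point holds as a gap in specification with a possible bias. The validity of the only efficacy estimator rests on an unstated assumption of completely random dropout, and the attrition check does not feed back into the estimate.

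It would be too strong to say that pain-related dropout will bias the group-by-time contrast. That contrast is about unbiased when observed severity drives dropout alike in both arms; what suffers then is the within-group change tests.

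Under the stated assumptions and independence, between-arm bias on disability is about 0.1 points (one arm) to 0.2 points (opposite patterns, a worst case) at the plan's correlation, with type I error of 5-6%. At an assumed correlation of 0.7 it is about 0.36 to 0.73 points, with type I error of about 9-10% to 23%. These sizes rest on the assumed odds ratio of 2, the assumed timing of dropout and the independence structure. The plan should be corrected, but the point does not by itself undermine the trial.

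**What to change.** Fit the same group-by-time and within-group contrasts with a likelihood mixed model for repeated measures, with unstructured covariance over T1 to T3, in the SAS already planned. This stays valid when dropout depends on observed outcomes, given a correct model.

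Alternatively keep GEE, name a working correlation other than independence, and add either inverse-probability-of-dropout weights or multiple imputation, using baseline pain and the SCPBI score.

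In either case, state the missing-data assumption and add one delta-adjusted sensitivity analysis for dropout related to unobserved pain, because neither route covers that case.

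The cost is revised wording and modest programming, with no change to visits, measures or sample size. The drawback is reliance on a covariance model or a dropout model, which the delta-adjusted analysis only partly offsets.

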### 1.2. Hypotheses to be tested:

Youth who receive *iCanCope with Sickle Cell Pain* will achieve greater increases in adaptive coping and significant reductions in symptoms of pain and pain-related disability (primary outcomes) as well as significant improvements in physical and emotional functioning and disease-specific health-related quality of life (secondary outcomes) at post-treatment and 6-month follow-up compared to youth who receive the attention-control condition. Feasibility and acceptability will be demonstrated by high levels of treatment engagement and high ratings of satisfaction with the intervention.

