Both groups will complete baseline (T1) measures online prior to randomization. Participants will be randomly allocated to either the experimental (*iCanCope with Sickle Cell Pain*) or attention control education group. Following program completion at 2 months (T2), participants will be asked to complete post-test measures. Electronic and SMS text reminders will also be sent by the study team. Participants will be asked to complete the same measures at 6 months (T3) following completion of the intervention or control condition. All measures will be completed online, either at home or in clinic. Paper versions of measures will be available if online access is not possible. Participants in both groups will be able to contact staff for technical problems with the app or website. Research staff will also be available at routine clinic visits during the study period.

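### Aim 1 compares change from baseline between arms with no stated baseline adjustment; read as the usual model, with 20% attrition and equal SDs, this gives up about 8–35% of the information at T2

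*Combined protocol and SAP*

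**What the plan says.** Section 14.1, Analytic plan for Aim 1, sets the model: "To account for clustering due to repeated assessments within individuals, generalized estimating equations (GEE) will be used". The between-arm test follows: "Interaction terms will be used to compare the mean change from pre-treatment to post-treatment" in one arm with that in the other. Within each arm, "Single degree of freedom contrasts will test if there is a statistically significant change in pain and coping" up to the end of treatment, and further contrasts look for a "statistically significant mean change from baseline to the 6-month follow-up for each group". Section 14.1 prints no model equation for Aim 1 and states no baseline covariate, common T1 mean or working correlation.

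Four other statements bear on this:

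- Section 5.2 (Both Groups) has participants complete the T1 "measures online prior to randomization".
- Section 1.2 hypothesises benefit "at post-treatment and 6-month follow-up compared to youth who receive the attention-control condition".
- Section 14.1 commits to an "intent-to-treat analysis including all randomized subjects".
- Section 10.4 says "With attrition conservatively estimated at 20% we expect a final sample size of 128", from 160 enrolled.

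**The concern.** T1 precedes randomisation, so any T1 difference between arms is chance. The usual group + time + group-by-time model still estimates that difference freely and subtracts it in full from the T2 difference. A model that knows the expected T1 difference is zero subtracts only the part that predicts T2, and so has a smaller variance. What is at stake is the width of the interval for the between-arm contrast, which is a main product of a pilot with about 64 followed per arm. Bias and type I error are not at stake.

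The text also leaves the model open. One with time and group-by-time terms but no group term already imposes a common T1 mean and, with a suitable working correlation, loses nothing. Two analysts could follow section 14.1 and report intervals of different width.

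**Working it through.** **Inputs.** Section 10.4 gives 160 enrolled and 128 followed. With equal arms, as in its power calculation, that is 80 and 64 per arm. It also gives, for pain, SD 2 and AR(1) with ICC 0.2. Assumed here: all 20% attrition occurs by T2 (the plan does not split it between T2 and T3), dropout is unrelated to outcome, and the T1–T2 correlation r runs from 0.2 to 0.8. The value 0.2 reads the plan's ICC as that correlation.

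**The plan's own figure.** The average of three AR(1) measurements has SD 2 × √[(3 + 4×0.2 + 2×0.2²)/9] = 1.313. With 49 per arm the SE is 1.313 × √(2/49) = 0.265. Two-sided power at a difference of 0.75 is Φ(0.75/0.265 − 1.96) = 80.7%, against 80% stated, so the pain figure reproduces. The disability figure does not (49% against 84% for a difference of 1.0). That is a separate matter, and the information loss below does not depend on the SD used.

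**Variance of the T2 contrast.** Set T2 SD = 1 and T1 SD = k. Per arm:

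- baseline-adjusted or common T1 mean: (1 − r²)/64
- planned, unstructured working correlation: (1 − r²)/64 + (r − k)²/80
- planned, independence working correlation: 1/64 + k²/80 − 2rk/80

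At k = 1 and r = 0.2, the adjusted variance is 0.96/64 = 0.0150. The planned variance is 0.0150 + 0.64/80 = 0.0230. The ratio is 0.652, a loss of 35%. The half-width for pain is 1.96 × 2 × √(2 × per-arm variance).

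| r (k = 1) | Adjusted | Planned, unstructured | Loss | Half-width, planned v adjusted | Loss if planned model uses independence |
|---|---|---|---|---|---|
| 0.2 | 0.01500 | 0.02300 | 35% | 0.84 v 0.68 | 35% |
| 0.5 | 0.01172 | 0.01484 | 21% | 0.68 v 0.60 | 25% |
| 0.8 | 0.00563 | 0.00613 | 8% | 0.43 v 0.42 | 31% |

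For the plan's pain difference of 0.75, T2 power is 42% planned against 58% adjusted, 59% against 69%, and 92% against 94%.

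**Sensitivity** (losses at r = 0.2, 0.5, 0.8; unstructured):

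- Same participants at both visits, k = 1: the loss is (1 − r)/2, that is 40%, 25%, 10%.
- 10% attrition by T2, k = 1: 38%, 23%, 9%.
- T1 SD/T2 SD = 0.8: 23%, 9%, 0%.
- T1 SD/T2 SD = 1.25: 48%, 38%, 31%.
- T3 contrast under AR(1) with 64 followed at both visits, k = 1: about 43%, 32%, 15%.

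**Simulation** (8000 runs, SD 2, k = 1). The SD of the T2 contrast, planned unstructured against common T1 mean, was 0.422 v 0.345, 0.348 v 0.309 and 0.222 v 0.212. The losses are 33%, 21% and 8%, in line with the formulas.

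**The case against.** Group-by-time is a standard, valid analysis. It matches hypotheses worded as increases and reductions, and section 2.2 reports the earlier Web-MAP trial in the same way. The text shows an under-specified model rather than a demonstrably inefficient one. The size of the loss is also uncertain:

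- The ICC of 0.2 is a planning value for an average over three time points, not an estimate for this contrast.
- The only repeat-measure correlation in the documents is 0.80 (section 2.2), for the pain burden interview. At that value, with equal SDs and unstructured correlation, the gain is negligible.
- Entry requires a minimum pain burden score (section 9.1), which would tend to shrink the T1 SD and so the loss. Nothing in the documents supports the 1.25 ratio.
- In a pilot seeking preliminary efficacy, a wider interval does not make the conclusion wrong.

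Much of this stands. The issue is precision only, the documents cannot place the trial between negligible and material, and the no-group-term reading is possible though less natural. It does not rescue the text as written. With equal expected T1 means, the difference in change and the baseline-adjusted difference estimate the same quantity, so the hypothesis wording does not favour the wider interval. In no scenario computed is the common-T1-mean analysis, with its covariance properly modelled, less precise. A high correlation protects the planned model only if the working correlation is right: under independence it still loses 31% at r = 0.8, and the plan does not rule that out.

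**Conclusion.** The point holds as a precision issue that should be fixed. Read as the usual model, with 20% attrition by T2, equal T1 and T2 SDs and dropout unrelated to outcome, the planned T2 contrast gives up about 8–35% of its information for r from 0.8 down to 0.2. The plan's own planning value sits at the 35% end. Let the SD ratio vary from 0.8 to 1.25 and the range widens to 0–48%. The arithmetic is firm; where this trial falls in the range is not known.

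There is a related gap. For pain and coping, section 14.1 describes the 6-month contrasts only within each arm, whereas section 1.2 hypothesises a difference from control at 6 months.

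**What to change.** In section 14.1:

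1. Model T1, T2 and T3 as outcomes with a common T1 mean across arms (time and group-by-time terms, no group effect at T1).
2. Name the between-arm contrasts at T2 and at T3.
3. State an unstructured working correlation for GEE, or use a likelihood-based mixed model with unstructured covariance in SAS, which the plan already names.

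This keeps every randomised participant with baseline data and still gives the planned within-arm change tests. At equal SDs their standard errors fall by 9%, 5% and 2% at r = 0.2, 0.5 and 0.8.

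Entering T1 as a covariate with T2 and T3 as outcomes is acceptable for the between-arm contrast only. It drops participants with no follow-up and does not directly give the within-arm tests.

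The cost is a short paragraph and a changed model statement, with no new data or visits. The one downside is reliance on a modelled covariance. Under independence the common-T1-mean model reduces to the raw T2 difference, which loses r² of the information (4%, 25% and 64%) against the adjusted estimate, so the covariance must be stated together with the constraint.

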### **3. Study Endpoints**

#### **3.1. Primary and secondary endpoints:**

Primary endpoint is greater reductions in pain-related disability. Secondary endpoint is the reduction of pain and anxiety/depressive symptoms.

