**5. Procedures Involved**

**5.1. Study design:**

A multi-site parallel group pilot RCT of *iCanCope with Sickle Cell Pain* versus *Attention Control Education* will be conducted with 160 youth (age 12-18) with SCD and their caregiver. The sites will include Emory/CHOA, The Hospital for Sick Children, and Connecticut Children's Medical Center, University of Mississippi, University of Florida, Boston Medical Center, Ann & Robert H. Lurie Children's Hospital of Chicago, Nationwide Children's Hospital, C.S. Mott Children's Hospital and Seattle Children's Hospital. Participants will be randomized into one of two groups; experimental group or attention control group. The intervention phase will last 6-8 weeks, with participants given a maximum of 12 weeks to complete the intervention content. This treatment period is based upon the typical duration of chronic pain intervention trials. Outcome assessment will occur at baseline (T1), immediately after completion of the intervention (2 months; T2), and repeated at 6 months post-intervention (T3) to allow for assessment of maintenance of treatment gains as youth with SCD may have fluctuations in their disease course that influence pain outcomes.

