**5.4. Data to be collected, including long-term follow-up data:**

Outcome data are self-report and will be collected online using the study website (Table 5). All measures have evidence of reliability and validity in youth in this age range, and include the core measures recommended for pain clinical trials. T1 = pre-treatment; T2 = post-treatment (2 months); T3 = follow-up (6 months post-treatment).

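### Section 14.1 names no between-arm test of the primary outcomes at 6 months, although the hypothesis is comparative; the only 6-month tests it names for them are within each arm

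*Combined protocol and SAP*

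**What the plan says.** - **Hypothesis (section 1.2).** Gains on the primary and secondary outcomes are expected "at post-treatment and 6-month follow-up compared to youth who receive the attention-control condition".
- **Time points (section 5.4).** "T2 = post-treatment (2 months); T3 = follow-up (6 months post-treatment". Post-treatment and 6-month follow-up are therefore separate assessments.
- **Between-arm test (section 14.1, Analytic plan for Aim 1).** "Interaction terms will be used to compare the mean change from pre-treatment to post-treatment for the" iCanCope arm with the change in the control arm.
- **6-month test (same section).** After within-arm contrasts at T2 for pain and coping, the plan adds that "additional contrasts will be computed to test if there is a statistically significant mean change from baseline to the 6-month follow-up for each group".
- **Secondary outcomes (same section).** GEE will be used to "test significant mean changes over time and between groups by using interaction terms and contrasts", with no time point given.
- **Purpose of T3 (section 5.1).** The assessment is repeated "to allow for assessment of maintenance of treatment gains as youth with SCD may have fluctuations in their disease course that influence pain outcomes".
- **Power (section 10.4).** The pain calculation is for a "difference of 0.75 in pain intensity (average over three time points").
- **Endpoint (section 3.1).** "Primary endpoint is greater reductions in pain-related disability", again with no time point.

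**The concern.** Half of the stated hypothesis concerns the difference between arms at 6 months, and section 14.1 gives that half no test that answers it. The tests it does name at T3 ask whether each arm has changed since baseline.

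Change within an arm can occur without any treatment effect. Section 5.1 itself says that the disease fluctuates and that this influences pain. Section 9.1 admits only youth who score at least 4 on the pain burden interview, so some regression towards the mean is plausible. Section 5.2 says the control condition is there to absorb effects of time, attention and computer use, and a per-arm test discards that protection.

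The plan does not say that significance in one arm will be taken as efficacy. But if only the named tests are reported, a reader has nothing else to go on at 6 months. An analyst following the text would also be free to decide, after seeing the data, whether to report a T3 comparison.

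**Working it through.** **1. Does any other section supply the test?**

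- *Aim 1 interaction:* change from pre- to post-treatment. Sections 1.2 and 5.4 both separate post-treatment from the 6-month follow-up, so this is T2.
- *Aim 1 contrasts at T3:* change for each group, so within-arm.
- *Secondary-outcome sentence:* between-arm, but limited to secondary outcomes and with no time point.
- *Aim 2 model:* whether a mediated effect of time differs by arm.
- *Aim 3 model:* an exploratory moderator-by-group-by-time term, which tests effect modification.
- *Section 10.4:* between-arm differences using three assessments, for pain expressly their average. This is a sample-size basis and not a T3 contrast.

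None is a between-arm test of a primary outcome at T3.

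**2. The plan's own power figure, to fix the inputs.** Section 10.4 for pain gives 49 per arm, difference 0.75, SD 2, AR(1), ICC 0.2, alpha 0.05 and power 80%. Read ICC 0.2 as the lag-1 correlation. The SD of the three-point mean is then 2 × √[(3 + 4×0.2 + 2×0.2²)/9] = 2 × 0.657 = 1.313. The SE of the difference is 1.313 × √(2/49) = 0.265, and two-sided power is 80.7%. The pain figure reproduces. (The disability figure does not: the same method gives 49.3% against the stated 84%. That is a separate matter and nothing below rests on it.) Under this reading the T1–T3 correlation is r = 0.2² = 0.04.

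**3. What per-arm tests would show if both arms improved equally.**

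Inputs: SD 2 and 128 completers from section 10.4. Assumed: an equal split (64 per arm), r from 0.04 to 0.7, and a common true improvement d from 0 to 1.0. The plan gives no values for r at T3 or for d.

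- SE of T3−T1 change in one arm = 2 × √[2(1−r)/64], which is 0.346, 0.316, 0.250 and 0.194 for r = 0.04, 0.2, 0.5 and 0.7.
- Chance of significant improvement in one arm: f = P(Z > 1.96 − d/SE).
- Chance that iCanCope alone is significant, with independent arms: f(1−f).

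Example, d = 0.5 and r = 0.5: d/SE = 2.00, f = 0.516, f(1−f) = 0.250.

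| Common change d | r = 0.04 | r = 0.2 | r = 0.5 | r = 0.7 |
|---|---|---|---|---|
| 0 | 2.4% | 2.4% | 2.4% | 2.4% |
| 0.25 | 10% | 11% | 14% | 19% |
| 0.5 | 21% | 23% | 25% | 20% |
| 0.75 | 24% | 22% | 13% | 3% |
| 1.0 | 15% | 10% | 2% | 0.1% |

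A two-sided 0.05 between-arm test gives a favourable false positive 2.5% of the time, whatever d is. Disability has SD 4, twice that of pain, so the same table applies to it with each common change doubled (0, 0.5, 1.0, 1.5, 2.0).

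**4. Power of the missing contrast, 64 per arm, two-sided 0.05.** SE of the difference in change = SD × √[2(1−r)] × √(2/64).

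| | r = 0.04 | r = 0.5 | r = 0.7 |
|---|---|---|---|
| Pain: SE | 0.490 | 0.354 | 0.274 |
| Pain: power for 0.75 | 33% | 56% | 78% |
| Disability: SE | 0.980 | 0.707 | 0.548 |
| Disability: power for 1.0 | 17% | 29% | about 45% |

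The 95% CI half-width (1.96 × SE) is about 0.5 to 1.0 for pain and 1.1 to 1.9 for disability.

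**The case against.** The strongest reply is that this is a drafting gap and the design already allows for the test. A GEE on three assessments with group-by-time terms yields a T3 contrast as a matter of course. The plan says secondary outcomes will also be examined between groups, which suggests that the primary outcomes get the same treatment. Section 10.4 powers both pain and disability as between-arm differences using all three assessments. The trial is a pilot seeking preliminary efficacy, its T2 comparison is intact, and the harm above needs a misreading that the plan does not commit.

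Much of this is fair. The contrast is available and not excluded, and the table describes a possible misreading with assumed inputs. It also runs below the nominal rate in places: at d = 1.0 it gives 2% and 0.1% for the two higher correlations. But none of these points names the test. Where the plan is specific about 6 months, it specifies a within-arm one.

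A second objection is that the documents disagree on what is primary. Section 3.1 makes disability primary and pain secondary, while section 1.2 and Table 5 also count pain and coping. That is true, and the gap exists under every version. The 6-month clause names no outcome, and the T2 contrasts before it name only pain and coping. If the clause is confined to those two, disability has no named 6-month test of any kind.

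**Conclusion.** The point holds. For the primary outcomes the plan names no between-arm test at 6 months, and the tests it does name there cannot answer the hypothesis in section 1.2. This conclusion rests on the text alone.

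The consequence is less certain. If per-arm significance were read as efficacy, the false-positive rate could lie anywhere from well below the nominal 2.5% to about ten times it (25% / 2.5% = 10). Where it falls depends on the common change and the T1–T3 correlation, neither of which the plan gives, and on the assumed equal split. The point should be fixed, but it leaves the design and the T2 comparison untouched.

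**What to change.** In section 14.1, for each primary outcome (pain intensity, pain-related disability and coping, once sections 1.2, 3.1 and Table 5 agree on the list):

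1. Name a single-degree-of-freedom group-by-time contrast from the planned GEE that compares baseline-to-T3 change between arms. Report its estimate and 95% CI as the test of the 6-month hypothesis.
2. Label the within-arm changes at T2 and T3 as descriptive and not as evidence of a treatment effect.
3. State whether T2 or T3 is the main time point.

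The cost is a few sentences and one more contrast per outcome, with no new data or visits. The drawback is the low power shown above, so the contrast should be read mainly through its CI. Adjusting for baseline would help if the correlation is low: SE = SD × √(1−r²) × √(2/64), which at r = 0.04 is 0.353 for pain (power 56% against 33%) and 0.707 for disability (29% against 17%). That is a different model specification and would have to be stated in advance.
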